5.2.3 Assessment of safety laboratory parameters

For the assessment of laboratory parameters, blood and urine samples will be collected by the trial site at the time points indicated in the [Flow Chart](#) after the subjects have fasted for at least 10 h. Overnight fasting is not required at the discretion of the investigator or designee for retests and for time points planned to occur after a meal.

The parameters that will be determined are listed in [Tables 5.2.3: 1](#) and [5.2.3: 2](#). Reference ranges will be provided in the ISF, Section 10.

Manual differential white blood cell count or urine sediment examinations will only be performed if there is an abnormality in the automatic blood cell count or in the urinalysis, respectively.

Though not necessary for clinical management, timed blood will be drawn from subjects that experience hypersensitivity or infusion reactions to help determine whether these were immune- or non-immune mediated. In accordance with clinical guidelines ([R15-5401](#)), such samples will be taken as soon as possible (without interfering with emergency treatment), preferably within 1-2 hours, but not later than 4 hours after onset of the reaction for the determination of tryptase, histamine, cytokines and complement ([R15-5400](#)). For details refer to [Table 5.2.3:1](#). A further blood sample will be drawn 12-24 hours later after resolution of symptoms as a baseline reference.

The routine safety laboratory and exclusionary tests listed in [Table 5.2.3: 1](#) and [5.2.3: 2](#) will be performed at _____ with the exception of the drug screening tests and Quantiferon analysis. Drug screening tests will be performed at the trial site using "Alere Triage TOX Drug Screen". Quantiferon TB-Gold test as well as additional laboratory tests in case of potential systemic hypersensitivity or infusion reaction or incipient albuminuria (see [Table 5.2.3:1](#)) will be done at _____ and _____, respectively.

Laboratory data will be transmitted electronically from the laboratory (_____) to the trial site or via paper print-outs).

Table 5.2.3: 1 Safety laboratory tests

Functional lab group	Test name	SCR	Day -5 to -1	Within period	End-of-trial
Haematology	Haematocrit	X	X	X	X
	Haemoglobin	X	X	X	X
	Red blood cell count (RBC)	X	X	X	X
	Reticulocyte count	X	X	X	X
	White blood cell count (WBC)	X	X	X	X
	Platelet count	X	X	X	X
	Glycated haemoglobin A1c (HbA1c)	X	-	-	-
Automatic WBC differential (relative and absolute)	Neutrophils	X	X	X	X
	Eosinophils	X	X	X	X
	Basophils	X	X	X	X
	Monocytes	X	X	X	X
	Lymphocytes	X	X	X	X
Manual WBC differential (if automatic is abnormal)	Polymorphnuclear neutrophils (segs)	X	X	X	X
	Band neutrophils (stabs)	X	X	X	X
	Eosinophils	X	X	X	X
	Basophils	X	X	X	X
	Monocytes	X	X	X	X
	Lymphocytes	X	X	X	X
Coagulation	Activated partial thromboplastin time (aPTT)	X	X	X	X
	Prothrombin time (Quick's test and INR)	X	X	X	X
	Fibrinogen	X	X	X	X
	Antithrombin III	X	-	-	-
	Protein S	X	-	-	-
	Protein C	X	-	-	-
Enzymes	Aspartate transaminase (AST/GOT)	X	X	X	X
	Alanine transaminase (ALT/GPT)	X	X	X	X
	Alkaline phosphatase (AP)	X	X	X	X
	Gamma-glutamyl transferase (GGT)	X	X	X	X
	Creatine kinase (CK)	X	X	X	X
	CK-MB, only if CK is elevated	X	X	X	X
	Lactate dehydrogenase (LDH)	X	X	X	X
	Lipase	X	X	X	X
	Amylase	X	X	X	X
Hormones	Thyroid stimulating hormone (TSH)	X	-	-	-
	Insulin	-	X ¹	X ¹	-
Substrates	Plasma glucose	X	X	X	X
	Serum creatinine	X	X	X	X
	eGFR (CKD-EPI for creatinine)	X	X	X	X
	Cystatin C	X	X	X	X
	Total bilirubin	X	X	X	X
	Direct bilirubin	X	X	X	X
	Total protein	X	X	X	X
	Albumin	X	X	X	X
	C-Reactive Protein (CRP)	X	X	X	X
	Uric acid	X	-	-	X
	Total cholesterol	X	-	-	X
	Triglycerides	X	-	-	X

1 Only on study days with oral glucose tolerance test (see [Flow Chart](#) and [Section 5.2.3.1](#))

Table 5.2.3: 1 Safety laboratory tests (cont).

Functional lab group	Test name	SCR	Day -5 to -1	Within period	End-of-trial
Electrolytes	Sodium	x	x	x	x
	Potassium	x	x	x	x
	Chloride	x	x	x	x
	Calcium	x	x	x	x
Urinalysis ¹ (Stix)	Urine nitrite	x	x	x ¹	x
	Urine protein	x	x	x ¹	x
	Urine glucose	x	x	x ¹	x
	Urine ketone	x	x	x ¹	x
	Urobilinogen	x	x	x ¹	x
	Urine bilirubin	x	x	x ¹	x
	Urine erythrocytes	x	x	x ¹	x
	Urine leukocytes	x	x	x ¹	x
	Urine pH	x	x	x ¹	x
Urine sediment ¹ (microscopic examination if erythrocytes, leukocytes nitrite or protein are abnormal in urine)	Only positive findings will be reported (for instance, the presence of sediment bacteria, casts in sediment, squamous epithelial cells, erythrocytes, leukocytes)	x	x	x ¹	x
Spot urine ^{1,2}	Creatinine	x	x	x ¹	x
	Albumin	x	x	x ¹	x
	Albumin to creatinine ratio	x	x	x ¹	x
Additional laboratory tests in case of potential systemic hypersensitivity or infusion reaction	Serum tryptase	-	-	x ³	-
	Histamine	-	-	x ³	-
	IL-2	-	-	x ³	-
	IL-4	-	-	x ³	-
	IL-6	-	-	x ³	-
	IL-8	-	-	x ³	-
	IL-10	-	-	x ³	-
	IL-12	-	-	x ³	-
	TNF α	-	-	x ³	-
	IFN γ	-	-	x ³	-
	C3a	-	-	x ³	-
C4a	-	-	x ³	-	
C5a	-	-	x ³	-	

1 Not required at time point 4:00 on Day 1

2 Preferably 2nd morning urine

3 Only in case of a potential systemic hypersensitivity or infusion reaction; sampling as soon as possible after onset of event and approx. 12h to 24h after resolution of event

The tests listed in [Table 5.2.3: 2](#) are exclusionary laboratory tests which may be repeated as required. The results will not be entered in the CRF/database and will not be reported in the CTR. Except for drug screening, it is planned to perform these tests during screening only.

Drug screening will be performed at screening and at the start of the inhouse period prior to drug administration on Day 1.

Table 5.2.3: 2 Exclusionary laboratory tests

Functional lab group	Test name
Drug screening (urine)	Amphetamine
	Barbiturates
	Benzodiazepine
	Cannabis
	Cocaine
	Opiates
Infectious serology (blood)	Hepatitis B surface antigen (qualitative)
	Hepatitis B core antibody (qualitative)
	Hepatitis C antibodies (qualitative)
	HIV-1 and HIV-2 antibody (qualitative)
	Quantiferon TB-Gold

To encourage compliance with alcoholic restrictions, a breath alcohol test (Alcotest[®] 6510 and Alcotest[®] 5510, Dräger, Belgium) will be performed at admission to trial site on Day -1, and may be repeated at any time during the study at the discretion of an investigator or designee. The results will not be included in the CTR.

5.2.3.1 Oral glucose tolerance test (oGTT)

An oGTT will be performed on the morning of Day -5 to -1 (baseline) and Day 29. After blood drawing for determination of fasting plasma glucose and serum insulin, 75 g of glucose will be dissolved in 200 mL water and swallowed by the subject. Thirty minutes, 1, 2 and 3 hours after intake of the glucose solution, further blood samples will be taken for glucose and insulin measurement. Blood samples for glucose measurements will be drawn in a 2 mL sodium fluoride (NaF) tube. Blood samples for insulin measurements will be drawn in a 2.5 mL serum tube.

5.2.3.2 Bleeding time

Bleeding time will be measured according to Duke Method at the time points given in the [Flow Chart](#). The subject will be pricked with a lancet in the earlobe, after having been swabbed with alcohol. The prick should be about 1.5-2 mm deep. Then the blood will be wiped every 30 seconds with a filter paper. The test ceases when bleeding ceases. The usual time is about 1-3 minutes. Abnormal findings will be reported as AEs (during the trial) or baseline conditions if judged clinically relevant by the investigator.

5.2.4 Electrocardiogram

5.2.4.1 12-lead resting ECG

Twelve-lead resting ECGs (I, II, III, aVR, aVL, aVF, V1 - V6) will be recorded using a computerised electrocardiograph (Cardionics SA, Brussels, Belgium) at the time points given in the [Flow Chart](#).

In order to achieve a stable heart rate at rest and to assure high quality recordings at comparable resting phases, all ECGs will be recorded for 10-sec duration after the subjects have rested for at least 5 min in a supine position. The site personnel will be instructed to assure a relaxed and quiet environment so that all subjects are at complete rest during the recordings. ECG assessment will always precede all other study procedures of the same time point (except blood drawing from an intravenous cannula which is already in place) to avoid impact of sampling on the ECG quality.

Electrode placement will be performed according to the method of Wilson, Goldberger and Einthoven. Precise electrode placement will be marked with an indelible mark on the skin to allow reproducible placement on day 1 and 2.

Triple ECGs (recorded within 180 sec) will be recorded at screening, as the baseline before drug administration and up to 30 hours after start of infusion. At all other time points single ECGs will be recorded.

All locally printed ECGs will be evaluated by the investigator or a designee.

ECGs may be repeated for quality reasons (like alternating current artefacts, muscle movements, electrode dislocation). For time points with triple ECGs, all three single ECGs will be repeated. For the repeats due to quality reasons, only the repeated ECG recordings will be used for analysis provided quality was better than with the initial ECG.

Additional (unscheduled) ECGs may be collected by the investigator for safety reasons. These ECGs are assigned to the prior scheduled time point. Unscheduled ECGs will not be included into the statistical analysis of interval lengths (if analysis is done).

For the inclusion or exclusion (see [Section 3.3](#)) of a subject and for the assessment of cardiac safety during the study, the QT and QTcB values generated by the ECG machines or their manual corrections by the investigators will be used. In doubtful cases, ECGs may be sent upfront for external evaluation. In this case, these externally measured results would overrule any other results obtained.

Abnormal findings will be reported as AEs (during the trial) or baseline conditions (at screening) if judged clinically relevant by the investigator. Any ECG abnormalities will be monitored carefully and, if necessary, the subject will be removed from the trial and will receive the appropriate medical treatment.

All ECGs will be stored electronically at site in order to enable a centralised re-evaluation of all 12-lead ECGs by an independent ECG laboratory if needed.

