Principal Investigator (or an authorised deputy) or the sponsor of the study, e.g. because of any unforeseen adverse events, etc. Dose escalation will only be permitted if no safety concerns exist in the opinion of the Principal Investigator (or an authorised deputy) and the Trial Clinical Monitor (or an authorised deputy).

The minimum data set for review consists of the following data (for the current dose group, safety data of at least 6 subjects having completed Day 8 will be required):

- AEs in the current and preceding dose groups (including clinically relevant findings from ancillary safety testing listed below) (Note: AEs may be ongoing at the time of Safety Reviews and AE information may be subject to change prior to Database Lock)
- Results from 12-lead EGG and continuous ECG monitoring in the current and preceding dose groups.
- Vital signs in the current and preceding dose groups
- Clinical laboratory tests in the current and preceding dose groups
- Preliminary PK/PD data for selected dose groups and time points as per [Section 7.3.4](#)
- Check of criteria for stopping subject treatment as per [Section 3.3.4.1](#)

The decision to escalate the dose will be made jointly by the Principal Investigator (or an authorised deputy) and the Trial Clinical Monitor (or an authorised deputy) after in-depth analysis of all available safety data, especially SAEs (if occurred), AEs and out-of-range laboratory results (if considered clinically significant).

Safety Reviews can be conducted face-to-face or by video/telephone conference. The investigator or project management team at the clinical site will be responsible for organization and minutes of the review meetings. Safety data will be provided and presented by the Principal Investigator (or an authorised deputy). Preliminary PK/PD will be provided by the sponsor as per [Section 7.3.4](#). Minutes will be signed off by the Principal Investigator (or an authorised deputy) and the Trial Clinical Monitor (or an authorised deputy) and filed in the ISF and TMF.

The investigator (after consultation with the sponsor) is allowed to alter the scheduled dose levels (e.g. add an intermediate dose level) within the planned dose range on the basis of experience gained during the study. In this case, the total number of subjects in this trial might increase. The investigator and/or the sponsor should stop dose escalation in case the safety evaluation leads to concerns that would not allow higher dosing.

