3.3.3 Exclusion criteria

Subjects will not be allowed to participate if any of the following general criteria apply:

1. Any finding in the medical examination (including BP, PR or ECG) is deviating from normal and judged as clinically relevant by the investigator
2. Repeated measurement of systolic blood pressure outside the range of 90 to 140 mmHg, diastolic blood pressure outside the range of 50 to 90 mmHg, or pulse rate outside the range of 45 to 90 bpm
3. Any laboratory value outside the reference range that the investigator considers to be of clinical relevance
4. Any evidence of a concomitant disease judged as clinically relevant by the investigator
5. Gastrointestinal, hepatic, renal, respiratory, cardiovascular, metabolic, immunological or hormonal disorders
6. Diseases of the central nervous system (including but not limited to any kind of seizures or stroke), migraine, and other relevant neurological or psychiatric disorders
7. History of relevant orthostatic hypotension, fainting spells, or blackouts
8. Chronic or relevant acute infections

9. History of relevant allergy or hypersensitivity (including allergy to the trial medication or its excipients)
10. Use of drugs (including any biological agent) with a long half-life (more than 24 h) within 30 days or less than 10 half-lives of the respective drug (whichever is greater) prior to administration of trial medication
11. Within 10 days prior to administration of trial medication, use of drugs that might reasonably influence the results of the trial or that might prolong the QT/QTc interval
12. Participation in another trial where an investigational drug has been administered within 60 days or 10 half-lives (whichever is greater) prior to planned administration of trial medication
13. Smoker
14. Ex-smoker who has stopped smoking less than one year prior to enrolment and/or who has a history of equal or more than 10 pack years
15. Alcohol abuse (consumption of more 30 g per day)
16. Drug abuse or positive drug screening
17. Blood donation of more than 100 mL within 30 days prior to administration of trial medication or intended donation during the trial
18. Intention to perform excessive physical activities within one week prior to administration of trial medication or during the trial
19. Inability to comply with dietary regimen of trial site

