20. A marked baseline prolongation of QT/QTc interval (such as QTc intervals that are repeatedly greater than 450 ms) or any other relevant ECG finding at screening
21. A history of additional risk factors for Torsades de Pointes (such as heart failure, hypokalemia, or family history of Long QT Syndrome)
22. Subject is assessed as unsuitable for inclusion by the investigator, for instance, because considered not able to understand and comply with study requirements, or has a condition that would not allow safe participation in the study

23. History of tuberculosis infection and/or a confirmed positive Quantiferon TB-Gold test
24. Subjects who in the investigator's judgement are perceived as having an excessive risk of thromboembolism (TE) for example because of a personal history and/or a first degree relative with a personal history with onset under the age of 55 of significant TE, including but not limited to deep vein thrombosis, pulmonary embolism, cortical sinus thrombosis, coronary and cerebrovascular events, cardiovascular disease, and peripheral arterial insufficiency
25. Abnormal results of coagulation values indicating an increased risk for bleeding or thromboembolism or complicating the safety evaluation during the study as determined by the investigator.
26. Deficiency of antithrombin III or protein S or protein C
27. Clinically relevant abnormal result of oral glucose tolerance test at baseline
28. Estimated glomerular filtration rate (eGFR) according to CKD-EPI formula < 90 mL/ min at screening ([R12-1392](#))

29. Urinary albumin/creatinine ratio (UACR) \geq 30 mg albumin / g creatinine at screening

For study restrictions, refer to [Section 4.2.2](#).

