3.3.4.2 Discontinuation of the trial by the sponsor

Boehringer Ingelheim reserves the right to discontinue the trial overall or at a particular trial site at any time for any of the following reasons:

1. New toxicological or clinical findings or serious adverse events invalidating the earlier positive benefit-risk-assessment. More specifically, the trial will be terminated if more

than 50% of the subjects show drug-related and clinically relevant adverse events of moderate or severe intensity, or if at least one drug-related serious adverse event is reported that is considered to be unacceptable.

2. The expected enrolment goals overall or at a particular trial site are not met
3. Violation of GCP, or the CTP, or the contract with BI by a trial site or investigator, disturbing the appropriate conduct of the trial
4. The sponsor decides to discontinue the further development of the investigational product.
5. Dose escalation will be stopped as soon as at least 2 subjects at one dose level on active drug showed relevant individual QT prolongation, i.e. a QTc increase of greater 60 ms from baseline in connection with absolute QT or QTc greater than 500 ms, which has been confirmed by a repeat ECG recording.
6. Dose escalation will be stopped based on the preliminary PK results as per [Section 7.3.4](#),

The investigator / the trial site will be reimbursed for reasonable expenses incurred in case of trial termination (except in case of the third reason).

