Changes in AUCs for glucose and insulin (oGTT measurements) from baseline to post-treatment will be compared between BI 655088 and placebo.

Descriptive statistics of bleeding time at the time points given in the [Flow Chart](#) and for the difference from baseline will be provided.

Descriptive statistics of vital signs and for the difference from baseline will be presented per planned time. ECG data will not be listed but clinically relevant abnormal findings will be reported as adverse events.

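### Section 5.2.4.1 uses QT and Bazett QTcB alone, so the >60 ms limb of the QT stopping rule can be met late when pulse falls well below baseline to about 50-55 bpm; let QTcF or QTcB satisfy it (minor)

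*Protocol*

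**What the plan says.** Protocol section 5.2.4.1 fixes the measure used both for eligibility and for on-study cardiac monitoring: "the QT and QTcB values generated by the ECG machines or their manual corrections by the investigators will be used". An ECG that leaves doubt may be read externally and that reading prevails, but no formula is named for it. The abbreviation list defines QTc as either the Fridericia or the Bazett value. QTcF is not mentioned elsewhere in the text at hand.

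Two rules depend on this choice.

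- **Entry (section 3.3.3).** Criterion 20 excludes marked baseline prolongation, with the example "such as QTc intervals that are repeatedly greater than 450 ms", or any other relevant ECG finding at screening. Criterion 2 excludes a repeated "pulse rate outside the range of 45 to 90 bpm".
- **Stopping escalation (section 3.3.4.2, item 5).** Escalation stops once "at least 2 subjects at one dose level on active drug showed relevant individual QT prolongation", defined as "a QTc increase of greater 60 ms from baseline in connection with absolute QT or QTc greater than 500 ms" and confirmed by a repeat ECG. Both parts must hold: the change and the absolute value.

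The Safety Review before each escalation (section 3.1) receives "Results from 12-lead EGG and continuous ECG monitoring in the current and preceding dose groups". Section 7.3.3 adds that "ECG data will not be listed but clinically relevant abnormal findings will be reported as adverse events".

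**The concern.** Item 5 is the numerical QT rule for stopping escalation in a first-in-human trial. It says only QTc, so section 5.2.4.1 makes it a Bazett rule. Bazett's correction depends more steeply on heart rate than Fridericia's. If a subject's pulse falls after baseline, part of a QTc rise disappears from the QTcB change.

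The raw QT limb does not remove this, because item 5 joins its two parts. A subject with QT above 500 ms at a slow pulse satisfies the absolute part but does not count until the QTcB rise also passes 60 ms. Two subjects are needed among six on active drug per dose level, so one subject who does not count could matter to the escalation decision.

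**Working it through.** **Inputs from the Protocol:** QT and QTcB (5.2.4.1); joint rule of >60 ms increase with QT or QTc >500 ms (3.3.4.2, item 5); 450 ms example and 45 to 90 bpm (3.3.3).

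**Assumptions:** the Protocol gives no baseline QTc and no expected pulse change. I take baseline QTcF of 390 to 420 ms and several illustrative pulse changes.

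**Formulas**, with RR = 60/rate in seconds:
- QTcB = QT/RR^(1/2); QTcF = QT/RR^(1/3); hence QTcB/QTcF = RR^(-1/6).
- Smallest QT meeting item 5 on QTcB: max[(QTcB0 + 60) × RR^(1/2), min(500, 500 × RR^(1/2))].
- The same on QTcF: max[(QTcF0 + 60) × RR^(1/3), min(500, 500 × RR^(1/3))].
- An either-formula rule takes the smaller of the two, so it can never fire later than the present rule.

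**When the change limb decides the timing.** Below 60 bpm the absolute part is met at raw QT 500 ms. The QTcB change limb is still unmet there if (QTcB0 + 60) × RR^(1/2) > 500, that is, if the rate is below 60 × ((QTcB0 + 60)/500)². For QTcB0 of 400, 410 and 420 ms this gives 50.8, 53.0 and 55.3 bpm. At QTcB0 of 440 ms it reaches 60 bpm.

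**One case in full: baseline QTcF 410 ms, pulse 75 to 50 bpm.**
- Baseline RR = 0.8, so QTcB0 = 410 × 0.8^(-1/6) = 410 × 1.0379 = 425.5 ms.
- On-drug RR = 1.2, RR^(1/2) = 1.0954, RR^(1/3) = 1.0627.
- Present rule: QT = max[485.5 × 1.0954, 500] = 531.9 ms, which is QTcF 531.9/1.0627 = 500.5 ms, a QTcF rise of 90.5 ms.
- QTcF rule: QT = max[470 × 1.0627, 500] = max[499.4, 500] = 500 ms, which is QTcF 470.5 ms.
- Delay: 500.5 - 470.5 = 30.0 ms on the QTcF scale.

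**Delay of the present rule against the either-formula rule (ms of QTcF), by baseline QTcF:**

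| Pulse, bpm | 390 | 400 | 410 | 420 |
|---|---|---|---|---|
| 75 to 50 | 8.6 | 19.3 | 30.0 | 31.2 |
| 60 to 50 | 0 | 3.7 | 14.0 | 14.8 |
| 75 to 55 | 0 | 0 | 6.9 | 17.5 |
| 65 to 55 | 0 | 0 | 0 | 7.0 |
| stable 50 | 0 | 0 | 1.3 | 1.9 |
| 75 to 60 | 0 | 0 | 0 | 0 |

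**Replacing QTcB instead of adding QTcF.** At baseline QTcF 410 ms, a QTcF-only rule fires at QTcF 500 ms in each case below:

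| Pulse, bpm | Present rule fires at QTcF | Delay from replacement |
|---|---|---|
| stable 65 | 493.4 | about 7 ms |
| stable 75 | 481.7 | about 18 ms |
| stable 80 | 476.6 | about 23 ms |
| 60 to 90 | 467.3 | about 33 ms |

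The either-formula rule adds no delay in any of these.

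**Entry example.** QTcB 450 ms equals 450/RR^(-1/6) in QTcF: 472 ms at 45 bpm (450/0.953), 464 at 50, 450 at 60, 434 at 75 and 421 at 90 (450/1.070). Conversely, QTcF 450 ms is QTcB 467 ms at 75 bpm and 481 ms at 90 bpm.

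**Obtaining QTcF.** RR = (QT/QTcB)², so QTcF = QT^(1/3) × QTcB^(2/3). Check: QT 531.9 and QTcB 485.5 return 500.5 ms.

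**The case against.** QTcB is a recognised correction, chosen explicitly, and it is the stricter one above 60 bpm, which is two thirds of the admitted pulse range (30 of 45 bpm). The slow-pulse scenario is assumed: nothing in the text at hand says the product lowers pulse. ECGs follow at least 5 minutes of supine rest, "In order to achieve a stable heart rate at rest", with triplicates at baseline and up to 30 hours. The raw QT limb covers much of the slow-pulse range, since QT 500 ms at 50 bpm is already QTcF 470.5 ms. Item 5 is also not the only gate. Escalation needs the agreement of the investigator and the trial clinical monitor after ECG review, subjects can be removed for relevant ECG changes, and doubtful ECGs can be read externally.

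Most of this stands and limits the point to a minor one. It does not remove it. Rest steadies the pulse during a recording but does not prevent a fall from baseline. The other safeguards are discretionary, and none calls for QTcF.

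Three stronger readings do not hold.

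- **That entry screening is unsafe.** The QTcF equivalent of 450 ms does shift by about 51 ms across the pulse range. But 450 ms is only an example, any other relevant finding excludes, raw QT is used too, and the investigator may exclude on judgement.
- **That item 5 is late at slow pulse in general.** At a stable 50 bpm the delay is 0 to 2 ms, and for 75 to 60 bpm it is nil. A marked fall from baseline is needed.
- **That a QTcF rise could never be seen later.** Section 7.3.3 rules out listing ECG data, but section 5.2.4.1 allows for a possible analysis of interval lengths and for central re-evaluation of stored ECGs. The statistical analysis plan is not at hand.

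**Conclusion.** The point holds as a cheap improvement of minor weight; the Protocol is not in error as written. With QTcB as the only correction, the change limb of item 5 can be met late when a subject's pulse falls well below baseline to about 50-55 bpm. For assumed baseline QTcF of 390 to 420 ms the size runs from nil to 31 ms, and delays near 30 ms need a fall of 25 bpm with a baseline of 410 to 420 ms. The pulse at which delay begins moves with the baseline. To change a decision, the masking would have to affect whether two active subjects at one dose level meet the rule, each with repeat-ECG confirmation. The direction of the effect and the conversion factors follow from the two formulas alone; the sizes depend on the assumed baselines and pulse changes.

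**What to change.** - **Section 5.2.4.1:** derive QTcF from the recorded QT and heart rate and use it alongside QTcB.
- **Section 3.3.4.2, item 5:** let the joint rule be met on either QTcF or QTcB, and keep the raw QT >500 ms limb.
- **Section 3.1:** show both QTcF and QTcB at the Safety Reviews.
- **Criterion 20, only if it is changed at all:** give the example as QTcF or QTcB repeatedly above 450 ms. Do not make QTcF the governing value, because that loosens entry above 60 bpm.

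The cost is protocol wording, with no extra ECGs. QTcF must be computed for dose groups already treated. There will be some extra flags: those QTcB raises at high pulse remain, and those QTcF raises after a pulse fall are added.
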